10.4.6. Secondary Efficacy Endpoints Analyses

Objective response rate (ORR) assessed by BIRC according to RECIST v1.1 will be analyzed as a key secondary endpoint. If both PFS and OS primary endpoints are positive, comparison between treatment groups in ORR by BIRC according to RECIST v1.1 will be performed using stratified Cochran-Mantel-Haenszel (CMH) test at 0.025 one-sided. Difference in proportions for ORR and its 95% CI using normal approximation will be provided. Overall response rates and their corresponding 95%

exact CIs will be calculated by Clopper-Pearson method.

The other time-to-event endpoints will be estimated using the Kaplan-Meier (KM) product-limit method, unless specified. A 95% CI for median survival time will be estimated by Brookmeyer-Crowley method, if necessary.

For other binary variables, stratified CMH test will be used and two-sided 95% CI for treatment difference will be calculated using normal approximation.

Further elaborations will be provided in the SAP.

10.4.7. Exploratory Endpoints Analyses

The time to deterioration (TTD) of EORTC QLQ-C30 endpoints will be analyzed using similar method for the primary endpoint OS (stratified Cox model and K-M curve). The scores of other scales and the average change from the baseline will be summarized using descriptive statistics by treatment cycle.

The correlation of the expression level of PD-L1 and proportion of strong expression of PD-L1 in tumor tissue with the efficacy of SHR-1210 combined with apatinib mesylate (including but not limited to ORR, OS) will be summarized using descriptive statistics. If necessary, an *ad hoc* analysis will be performed and results will be presented in a separate supplementary report.

Efficacy endpoints (e.g. BOR, ORR) and safety endpoints (e.g. immune-related adverse events (irAE), study drug-related AE with CTCAE grade ≥ 3 , drug-related SAE) with SHR-1210 ADA/Nab status in experimental arm will be summarized using descriptive statistics. If necessary, a comparison of efficacy and safety will be performed according to the ADA status.

PFS, TTP, ORR and DoR assessed by investigator based on RECIST v1.1 will be evaluated using the same analytical methods for the secondary endpoints.

Other analytical methods for exploratory endpoints will be elaborated in the SAP.

10.4.8. Handling of Missing Data

Except for the special cases, the following rules will be applied to the missing date of the events.

If the start date of the event is all missing, it will not be imputed. If the day is missing, but the year and month are consistent with the year and month of the study drug treatment, the day of the first study drug treatment will be used. Otherwise, the first day of the month will be used. If the day of end date is missing, but the year and month are consistent with the year and month of the end of study drug treatment, the day of end of treatment will be used. Otherwise, the last day of the month will be used.

If the month and day of the event are missing, but the year of occurrence is consistent with the year of study drug treatment, the month and day of the first study drug treatment will be used. Otherwise, January 1 will be used.

All imputation dates should be prior to the date of withdrew consent, lost to follow-up or death.

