10.4.9. Safety Analyses

10.4.9.1. Analyses of Adverse Events

Adverse events will be coded to MedDRA (v 18.1 or higher) for lower level term (LT), preferred term (PT) and primary system organ class (SOC).

A treatment-emergent adverse event (TEAE) is defined as an adverse event (AE) that had an onset date after the start of the study treatment or that worsened in severity from baseline (pretreatment).

Only those AEs that were treatment-emergent will be included in summary tables. All AEs, treatment-emergent or otherwise, will be presented in subject data listings.

The incidence of TEAEs will be reported as the number (percentage) of subjects with TEAEs by SOC and preferred term. A subject will be counted only once by the highest severity grade per NCI-CTCAE v4.03 within an SOC and preferred term, even if the subject experienced more than 1 TEAE within a specific SOC and preferred term. The number (percentage) of subjects with TEAEs will also be summarized by relationship to the study drug. Treatment-related AEs include those events considered by the investigator to be definitely, possibly related to study treatment or with missing assessment of the causal relationship.

Subject incidence of AE, SAE, AE with CTCAE Grade ≥ 3 , SAE with CTCAE Grade ≥ 3 , drug related AE, drug related SAE, AE with incidence $\geq 5\%$, SAE with incidence $\geq 5\%$, AE leading to dose adjustment, AE leading to discontinued treatment etc. will be tabulated by experimental arm. Time-to-adverse events of special interest, and duration of events will be analyzed using K-M method.

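### The AE date-imputation rules do not fit the treatment-emergent definition, and nothing keeps an imputed end date on or after onset (minor)

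*Protocol*

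**What the plan says.** Section 10.4.8 (Handling of Missing Data) sets the rules for incomplete event dates.

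- Onset wholly missing: "If the start date of the event is all missing, it will not be imputed".
- Onset with only the day missing, in the month of study drug treatment: "the day of the first study drug treatment will be used". In any other month, the first of the month.
- End with only the day missing, in the month treatment ended: the day treatment ended. In any other month, the last of the month.
- Year only: "If the month and day of the event are missing, but the year of occurrence is consistent with the year of study drug treatment", then "the month and day of the first study drug treatment will be used. Otherwise, January 1 will be used". The sentence does not say whether it covers onsets, ends or both.
- The only limit on an imputed date is that it must precede withdrawal of consent, loss to follow-up or death. The section also exempts special cases without naming them.

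Section 10.4.9.1 (Analyses of Adverse Events) calls an event treatment-emergent if it "had an onset date after the start of the study treatment", or if its severity worsened relative to the pretreatment baseline. It then states: "Only those AEs that were treatment-emergent will be included in summary tables". All AEs, whatever their status, go into subject listings. For AEs of special interest it plans a Kaplan-Meier analysis of time to event, and it adds that "duration of events will be analyzed using K-M method".

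**The concern.** The protocol fixes these rules in its own text, and they do not work together.

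An event with no onset date has nothing to compare with the start of treatment, and no default classification is given. An onset placed on the first-dose day is not later than that day when dates are compared without clock times, so an imputation evidently meant to keep the event on treatment can remove it. The same comparison catches fully recorded day-1 events. Section 5.1.6.2.4 expects allergic reactions mostly within 24 hours of infusion, and Section 8.4 makes infusion reactions of Grade 3 or above an event of special interest. A reaction on the day of the first infusion is therefore exposed.

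On end dates, Section 8.3 collects AEs until 90 days after the last SHR-1210 dose or 30 days after the last anti-angiogenic dose, whichever is later. Onsets after treatment has ended are expected, yet a day-missing end can be pulled back to the day treatment ended.

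At stake are the AE summary tables and the Kaplan-Meier analysis of event duration, which cannot use a negative time.

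**Working it through.** There is no stated figure to reproduce. The check applies the written rules to example dates. The dates are assumptions: first dose 12 March 2018, end of treatment 10 December 2018. The year-only comparison is read as the year of first dose.

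**Onset dates (Section 10.4.8) against the onset limb (Section 10.4.9.1)**

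| Recorded onset | Imputed onset | After first dose? | On or after? |
|---|---|---|---|
| nothing | none | cannot be evaluated | cannot be evaluated |
| March 2018 | 12 March 2018 | no | yes |
| 2018 | 12 March 2018 | no | yes |
| 12 March 2018 (complete) | not imputed | no | yes |
| June 2018 | 1 June 2018 | yes | yes |
| 2019 | 1 January 2019 | yes | yes |

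Changing the comparison to on or after repairs rows two to four. It does nothing for a wholly missing onset, which needs its own default.

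**End dates, day missing (the explicit end rule)**

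Onset 20 December 2018, end recorded as December 2018, end of treatment 10 December 2018. The end falls in the month treatment ended, so it becomes 10 December. Duration = 10 - 20 = -10 days. No disputed reading is needed.

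To see how often the rule misfires, take first dose on each of the 365 days of 2018, an assumed 180 days of treatment, onset on each of days 1 to 270 after first dose, and an end in the onset month with the day missing. That is 365 × 270 = 98,550 cases. The imputed end precedes onset in 5,373, and 5,373 / 98,550 = 5.5%. This is a share of cases that already have such an incomplete end date. It is not a forecast for the trial.

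**End dates, year only (only if the year-only rule is also used for ends)**

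- Onset 15 June 2018, end 2018: end becomes 12 March 2018, duration -95 days.
- Onset 1 February 2019, end 2019: end becomes 1 January 2019, duration -31 days.
- Onset 20 November 2018, end 2019: end becomes 1 January 2019, duration +42 days, which is possible.

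Over the same 98,550 cases with the end in the onset year, the imputed end precedes onset in 98,280 (99.7%). The other 270 have onset on 1 January 2019 and duration zero. If the rule is not used for ends, a year-only end has no rule at all.

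**Scale**

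Section 3.1 plans about 43 subjects: 1/43 = 2.3%, 2/43 = 4.7%, 3/43 = 7.0%. Section 10.4.9.1 tabulates AEs with incidence of at least 5%, so one subject can move a term across that line.

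**The case against.** The strongest reply is that exclusion is inferred from the wording and is not a stated rule. The treatment-emergent definition has a second limb, worsening from baseline, which needs no onset date and could readmit a reaction that was absent before treatment. An onset after the start of treatment can be read to include day 1 once the drug has been given. Both points stand, and they are why the conclusion is conditional. The AE tables should still not depend on which reading a programmer chooses.

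A reader might infer that affected events vanish from every safety table. The documents do not support that. The listings keep all AEs, and the laboratory, vital-sign, ECOG and ECG summaries in Sections 10.4.9.2 and 10.4.9.3 do not use AE dates.

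A reader might also infer that the protocol consistently settles unknowns towards lower toxicity. It does not: Section 10.4.9.1 counts an event with a missing causality assessment as treatment-related.

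Nor is it established that the year-only rule yields impossible end dates. Its wording, keyed to the year of occurrence and the first dose, leans towards onset. The -95 and -31 day results are conditional on using it for ends. The -10 day result is not.

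Finally, incomplete dates may be few. Sections 7.3.2 and 8.1.1 ask for AE timing, and Section 11.1.3 provides for repeated data queries. Each subject also counts once per term, so a lost record matters only if it was that subject's sole or worst event for the term. Section 10 lets the SAP supersede the protocol, so the SAP could settle all of this. That does not make the rules as written correct.

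**Conclusion.** The point holds as an inconsistency between two sections and a missing order check on imputed dates. Read literally on dates, AEs with a missing onset, those imputed to the first-dose day and those fully dated on day 1 fail the onset limb. They can leave the AE summary tables unless the worsening limb brings them back. The explicit day-missing end rule can give a negative duration, which would enter the planned Kaplan-Meier analysis.

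The size of the effect is unknown because the protocol gives no rate of incomplete dates; the only fixed scale is 2.3 percentage points per subject at 43. The conclusion rests on comparing dates without clock times and on the undefined special cases not already covering these events. The primary endpoint is not affected. Severity: minor.

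**What to change.** Amend Sections 10.4.8 and 10.4.9.1 as follows.

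1. Define a treatment-emergent AE as one with onset on or after the date of first dose (by clock time on day 1 where recorded), or one that worsens from baseline.
2. Treat an AE with missing or partial onset as treatment-emergent unless its known date parts or its end date show that it preceded first dose.
3. Limit the year-only rule (first-dose month and day, or 1 January) to onset dates.
4. Give year-only end dates their own rule, for example the earliest of 31 December, death, last contact and the end of the AE collection window.
5. Require every imputed end date, including a day-missing one, to be no earlier than onset.

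The cost is about two paragraphs of text, best settled before database lock. The downside is that a few pre-treatment events may be counted as treatment-emergent, which is the conservative direction for a safety summary.

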10.4.9. Safety Analyses

10.4.9.1. Analyses of Adverse Events

Adverse events will be coded to MedDRA (v 18.1 or higher) for lower level term (LT), preferred term (PT) and primary system organ class (SOC).

A treatment-emergent adverse event (TEAE) is defined as an adverse event (AE) that had an onset date after the start of the study treatment or that worsened in severity from baseline (pretreatment).

Only those AEs that were treatment-emergent will be included in summary tables. All AEs, treatment-emergent or otherwise, will be presented in subject data listings.

The incidence of TEAEs will be reported as the number (percentage) of subjects with TEAEs by SOC and preferred term. A subject will be counted only once by the highest severity grade per NCI-CTCAE v4.03 within an SOC and preferred term, even if the subject experienced more than 1 TEAE within a specific SOC and preferred term. The number (percentage) of subjects with TEAEs will also be summarized by relationship to the study drug. Treatment-related AEs include those events considered by the investigator to be definitely, possibly related to study treatment or with missing assessment of the causal relationship.

Subject incidence of AE, SAE, AE with CTCAE Grade ≥ 3 , SAE with CTCAE Grade ≥ 3 , drug related AE, drug related SAE, AE with incidence $\geq 5\%$, SAE with incidence $\geq 5\%$, AE leading to dose adjustment, AE leading to discontinued treatment etc. will be tabulated by experimental arm. Time-to-adverse events of special interest, and duration of events will be analyzed using K-M method.

10.4.9.2. Laboratory Tests Results

Clinical laboratory (eg, hematology, blood biochemistry) values will be evaluated as appropriate. Abnormal laboratory values will be flagged and identified as those outside (above or below) the normal range. Descriptive summary statistics (eg, n, mean, standard deviation, median, minimum, maximum for continuous variables; n [%] for categorical variables) for laboratory parameters and their changes from baseline will be calculated. Laboratory values will be summarized by visit and by worst post baseline visit.

Laboratory parameters that are graded in NCI-CTCAE v4.03 will be summarized by NCI-CTCAE grade. In the summary of laboratory parameters by NCI-CTCAE grade, parameters with NCI-CTCAE grading in both high and low directions will be summarized separately.

10.4.9.3. Others

The analyses of vital signs will include summary statistics of change from baseline over time by experimental arm.

The analyses of ECOG-PS will include summary statistics of baseline and highest score post baseline by experimental arm.

The analyses of ECG will include summary statistics of baseline and worst clinically abnormal grade post baseline by experimental arm.

10.4.10. Multiplicity

PFS hypothesis will be tested at $\alpha=0.005$ (one-sided) and OS hypothesis will be tested at $\alpha=0.02$ (one-sided). If either hypothesis is significant at its initial one-sided α level, its α will be re-allocated to the other endpoint to be tested at $\alpha=0.025$ one-sided. A nominal alpha of 0.01% will be spent on testing the OS hypothesis at the time of the planned PFS analysis. For the interim analysis (70% events) and final analysis of OS endpoint, the Lan-DeMets O'Brien-Fleming spending function was used to control the type I error.

When both the PFS analysis and OS (interim or final) analysis tests are significant, ORR assessed by BIRC according to RECIST v1.1 may be tested at 0.025 one-sided (alpha re-allocation).

Any changes to the above strategy will be documented elsewhere, if not in a protocol amendment, at the earliest time before any formal analysis is being conducted.

10.4.11. Subgroup Analyses

To determine whether the treatment effect is consistent across various subgroups, HR and 95% CI for the primary endpoints OS and PFS (assessed by BIRC base on RECIST v1.1) will be estimated and plotted within each category of the following classification variables:

- Age (<40 years vs. ≥ 40 years)
- Locations (extremities vs. axial skeleton)
- Gender (male versus female)
- Involved disease sites (1 vs 2 vs ≥ 3)
- Previous local therapy (including radiotherapy) (yes vs no)
- ECOG-PS Score (0 vs. 1).

10.5. Data Monitoring Committee

The study will establish a Data Monitoring Committee (DMC) to regularly assess safety data, and analysis will be conducted for assessment of efficacy and safety at the time of PFS analysis and OS interim analysis. The DMC will provide advice on the measures that must be taken for protection of subjects and overall safety evaluation to the sponsor.

The DMC is the consultant to the study team of the sponsor. The study team of the sponsor are responsible for overall conduction of the study, including management of the exchange and communication of study data, analysis based on the advice from the DMC, and making decisions on continuation of, amendment to or termination of the study.

After the study is initiated, the DMC will hold meeting to evaluate safety data on a regular basis, as to ensure the subject's safety is carefully supervised. The sponsor can also consult the DMC in a retrospective manner based on the safety signals discovered, and hold retrospective safety review meetings as required. The DMC can make recommendations for continuing, revising or terminating the study based on observed safety or efficacy data. Prior to the meeting, the DMC will look up and review the study data acquired, including the characteristics of the study population, dose information, safety and efficacy data in PFS analysis.

The composition, responsibilities, operation and management of the DMC will be detailed in a separate DMC charter.

11. DATA MANAGEMENT METHODS

11.1. Recording of Data

Electronic data capture system (EDC) will be used for collection and management of clinical study data in this study.

11.1.1. Recording of Source Document

The source document should be completely maintained as the original document in clinical trial. They should be filled in and maintained by investigators. The subject's information on the cover of the source document should be checked firstly prior to filling in each time, the handwriting should be legible and easy to read, so that the monitor from the sponser can check the data with eCRF.

11.1.2. Filling of eCRF

The data in eCRF comes from original documents such as medical record and laboratory examination report, and should be consistent with the original documents. Any observation and examination result during the trial should be filled in the eCRF promptly, correctly, completely, standardized and truthfully.

The reason for data modification needs to be filled in accordance with the system implication, when the data in eCRF are corrected.

11.1.3. eCRF Review

Investigators should fill in, save and submission of eCRF promptly after the end of each visit. The system logic verification program will check the integrity and logic of the data entered in EDC system, and query the problem data. The principal investigator or data entry personnel are allowed to modify or explain the problem data, and multiple queries can be raised until the problem data are resolved, when necessary. Monitors, data administrator and medical auditors will review eCRF data when necessary as well, and query the doubtful data. Investigators should respond to the queries from the system and data auditors in time. After completion of data clearance, investigators will sign the electronic signature of the completed eCRF.

11.2. Data Management

11.2.1. Establishment of EDC Database

Data administrator will establish study data collection system and database in accordance with the protocol, and provide on-line use prior to enrollment of the subject. All the EDC users need to complete relevant trainings, fill in the training records, and account application forms to obtain the corresponding account of the login system.

11.2.2. Data Review and Database Lock

Prior to lock of database, the project team need to summarize all the events of deviation from protocol during the trial, and hold data review meeting. Any decision made during the data review meeting should be documented.

After all data have been reviewed, lock of database will be confirmed by investigators, sponsor and statisticians. The data documents can not be modified after locking. Post-locking data need to be properly maintained for future reference.

11.2.3. Data Archiving

After completion of the study, subject's eCRF in a format of PDF should be generated in EDC system, and save it on in CD-ROM, and submit it to the sponsor and the organization to keep the file for inspection.

The storage and management of study documents must be performed in accordance with the requirement of GCP, investigators should inform the sponsor in advance when destroying any document or data related with the trial. The sponsor should keep the study documents until at least 5 years after approval of the investigational drug.

12. SOURCE DATA AND SOURCE DOCUMENT

According to the International Council for Harmonisation (ICH) E6, relevant regulations and study centers' requirements for the protection of subjects' personal information, each study center must keep records of treatment and research related to this study properly. As one part of the study funded or involved by Jiangsu Hengrui Medicine Co., Ltd., each study center should allow Jiangsu Hengrui Medicine Co., Ltd. or its authorized representative and regulatory authorities to audit (replicate if allowed by the law) the clinical records, as to perform quality review and audit, as well as evaluation of safety, study progress and data verification.

The source data are all the information necessary to reconstruct and evaluate clinical study, and are the original record of clinical findings, observations or other activities. Examples of these source documents and data include, but are not limited to: hospital records, laboratory records, memoranda, subject's diaries, pharmacy dispensing records, recording of consultation meetings, recording data of automated instruments, copies or transcriptions certified after verification as being accurate copies, microfiches, photographic negatives, microfilm or magnetic media, X-rays, and records kept at the pharmacy, at the laboratories and at medico-technical departments involved in the study.

13. QUALITY ASSURANCE AND QUALITY CONTROL

In order to ensure the quality of the trial, the clinical study plan is discussed and established by the sponsor and investigators prior to the official start of the trial. And they should confirm whether the personnel involved in the trial has received appropriate GCP training.

Each study site must manage the investigational drugs in accordance with SOP, including receiving, storage, dispensation, recovery and destroying (if applicable).

According to GCP guidelines, necessary procedures must be taken during the design and implementation of the study, to ensure that the collected data are accurate, consistent, complete and reliable. All the results and abnormal findings observed in the clinical trial should be verified and recorded promptly to ensure the reliability of data. The instruments, equipment, reagents and standard materials used in the clinical trial should have strict quality standards, and ensure that they are working under normal conditions.

The investigators input the required information into the eCRF, the monitors check the complete and accurate filling, and instruct the personnel at the study center for necessary modification and supplementation.

Drug regulatory authorities, Institutional Review Board (IRB)/Independent Ethics Committee (IEC), the Sponsor's monitors and/or auditors may conduct a systematic review of the clinical trial-related activities and documents to assess whether the trial has been conducted in accordance with the trial protocol, SOP and the requirements of relevant laws and regulations, and whether the trial data are timely, truthfully, accurately and completely recorded. The audit should be performed by the personnel who are not directly involved in the clinical trial.

